Patients identified as frequent ED users will undergo an alcohol use disorder screening conducted by the research case manager, PI, or research fellow using a validated screening tool, the Alcohol Use Disorder Identification Test (AUDIT) which constitutes the screening component of SBIRT. The AUDIT places patients into one of four categories: low risk, risky, harmful, and severe. Brief intervention and pharmacotherapy have previously been shown to be most effective in those with harmful or severe use disorders [12]. Patients found to have at least harmful alcohol use based on the screening will be offered enrollment (AUDIT score ≥ 8). Enrollees will have blood and urine samples collected to screen for active opiate use including fentanyl, platelet counts, pregnancy, or significant liver disease (see exclusion criteria below) if no results are available in EHR. With the exception of urine pregnancy screening these tests are done as part of the routine care of emergency department patients with alcohol use disorders who are interested in accessing treatment. The results will be used to confirm inclusion/exclusion criteria are met. Patients meeting all criteria will be enrolled into the study and will receive 380mg of extended-release naltrexone as an intramuscular injection in the ED.

Naltrexone training and administration:

Study staff will compose and send e-mail before the start of the study, with input from UCSF ED nursing leadership, to all ED RNs informing of the intent and responsibilities of the study. Subsequently, during RN sign out (twice daily at 7am and 7pm) study staff will remind ED RNs about the study protocol to ensure as much staff as possible is aware of RN involvement and responsibilities. The shift-change information session will be performed for a two week run in period to assure all RNs are oriented.

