The ED is staffed by clinical pharmacists 12-16 hours per day and will be present during study enrollment hours. They will be trained on the specifics of the study protocol by our [name], an ED pharmacist at our Parnassus ED. RNs will be able to consult [name] or any of the other ED pharmacists on the specifics of medication procurement, administration, and monitoring during the study period. Similarly, ED resident physicians and attending physicians will be informed of the study protocol and will receive didactic teaching about physician involvement and responsibilities via email and during resident conference and the monthly Department of Emergency Medicine faculty meeting.

Medication storage and distribution:

We will work with UCSF Investigational Drug Storage (IDS) to store all drug doses. The initial dose will be given in UCSF ED and for all doses, we will create a study-specific link in our electronic medical record system (Apex) for order entry, which will link to the study supply. Our study team will verify consent prior to verification and the study consent to be uploaded into Apex. IDS will generate an Rx form that can be used to request the subsequent clinic or other community-based doses (“clinic supply) drug for an enrolled subject.

The clinic supply will be labeled for the subject and picked up from UCSF IDS by study staff for transport to clinic or community site for administration. The clinic supply will be given 7-day expiration at room temperature from time of dispensing per FDA labeling. (Store unopened kit at 2°C to 8°C (36°F to 46°F). Kit may be kept at room temperature of $\leq 25^{\circ}\text{C}$ (77°F) for ≤ 7 days prior to use; do not freeze. Following reconstitution of the suspension, administer immediately) and the drug will be transported at ambient temperatures. Insulated cooler to be used if ambient temperature are expected to exceed 25C. If the clinic dose is not used, unused study drug will be returned to UCSF IDS for accountability and disposal.

Index ED visit:

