The case manager will obtain baseline data using a HIPAA compliant database REDCap used for multiple ongoing research studies at UCSF. Baseline data will be collected for the purposes of the study and for ongoing case management including information on where the patient lives or stays (if unhoused), contact information (phone numbers, family member contacts, email, etc.) and preferred mode of communication. Those without cellphones who choose to enroll and who agree will be provided with a cell phone at the time of enrollment for the purposes of maintaining touch with research case manager and research team. We will track the rate of cell phone issuance, loss, and use for study purposes as one of our feasibility metrics. The case manager will also use REDCap to collect a detailed substance use history using validated questions from the Addiction Severity Index (ASI), and assess social, occupational, and psychological alcohol related problems using the Short Inventory of Problems (SIP-2R). Alcohol use will be quantified using the timeline follow back method [18,19].

Index visit follow up:

The research case manager and the patient will coordinate a follow-up plan for the next injection visit. ED social workers routinely refer patients to case management and other outpatient services including drug and alcohol treatment programs. The facilitation of referral to ongoing care by the study case manager will simply represent a new option for securing outpatient follow-up for enrolled patients. This coordination of follow-up care will be outlined in the informed consent document and explained as a part of study enrollment.

Prior to leaving the ED after the index visit the research case manager will provide the patient with a medical bracelet or wallet card that identifies them as study participant using extended release naltrexone and provides the contact information for the PI and research case manager.

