The medical bracelet or wallet card will alert providers that opiate dosing adjustments may be necessary to adequately treat acute pain should the patient require treatment during the study period. It will provide information about the added precautions necessary should that patient require opioid pain management. Specifically, as the amount of opioid required to achieve adequate analgesia may be increased any resulting respiratory depression may be deeper and more prolonged. Therefore a fast acting agent is preferred and the amount of opioid analgesic should be titrated to the clinical effect in a setting equipped for cardiopulmonary resuscitation. The PI will be available by phone for emergency consultation at any time.

Visit 2-3 study procedures:

Patients will receive a monthly intramuscular injection of extended release naltrexone for up to 3 consecutive months during visits for which the research case manager will outreach to the participants in the community. Injections will be administered in an outpatient setting by an addiction community provider familiar with XR-Naltrexone, or in the UCSF ED depending on patient preference. A 20-dollar gift card incentive will be used to encourage follow-up at the time of each injection. We will follow participants for 12 months from the time of enrollment (an additional 9 months after the final dose of XR-NTX administered on behalf of the study). Specimens for alcohol biomarker testing will be collected at follow up visits.

At each of the monthly follow up visits we will collect data on a) feasibility measures and b) study outcomes. During the follow-up period, the research case manager will track all participants and we will continue to collect data on study outcomes using REDCap including ED and inpatient hospital use, substance use, readiness to change, and engagement in substance use recovery/rehabilitation via community treatment programs, as well as subsequent doses of XR-Naltrexone administered. This data will be collected by administering the same validated questionnaires used in the index visit (AUDIT, ASI, SIP-2R). The PI and research fellow will also query the EDIE system and UCSF EHR monthly in order to identify any emergency department visits that could be related to the study procedures.

Follow up procedures after visit 3:

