Because this is a feasibility study, primary outcomes of interest are recruitment (consent) rate, time required to complete initial tele-medicine assessment in the ED, time needed to administer XR-NTX in the ED, total ED length of stay, time to first follow up after the initial ED encounter, number of cell phones issued by the study, retention and follow up rates over the 3-month study

period, retention rate with other providers in San Francisco, number of doses of XR-NTX received during the study period and intervals between doses, and barriers to and facilitators of follow-up after the initial ED visit.

We will also collect pilot data on the following for statistical analysis:

Predictor Variable: Multi-modal treatment with Extended Release Naltrexone and case management

Primary Outcome: Change in the number of Emergency Department visits for alcohol-related complaints. [(# of ED visits for alcohol related complaint in 12 months after enrollment) - (# of ED visits for alcohol related complaint in 12 months before enrollment)].

Secondary Outcomes: number of standard alcoholic drinks consumed per week, number of days of heavy drinking, overall substance use severity (change in AUDIT score), change in alcohol-related social/occupational/psychological problems identified on SIP-2R, change in PEth, and change in urine ethyl glucuronide

Cost analysis: This study will not provide precise estimates of efficacy or costs. However, we will use our results to perform a basic cost analysis to guide future research. We will estimate: overall cost and cost per patient (medications, case management, follow-up visits), cost per avoided ED visit, cost per avoided hospitalization, program cost vs expected medical cost saved. All costs will be estimated at the societal perspective

Potential confounding variables or covariates, justifications:

There are several potential confounders which we will measure such as number of doses of XR-NTX received, willingness to change, engagement in other, baseline substance use severity, housing status, psychiatric and medical comorbidity, and basic demographic variables such as age and sex. The primary strategy employed to combat these cofounders is the selection of the primary outcome. Since the outcome is a change from the patient's baseline ED usage from the prior year each patient serves as their own control. Thus they are matched for many of the possible confounders.

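### Change in PEth and change in urine ethyl glucuronide are secondary outcomes, but no specimen for either is scheduled before the first injection

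*Combined protocol and SAP*

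**What the plan says.** The secondary outcomes in section IV (Analysis, Measurements, and Outcomes) end with "change in PEth, and change in urine ethyl glucuronide". No time points are attached, and neither marker is named anywhere else in the protocol.

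The one sentence on collection is in section II, Visit 2-3 study procedures: "Specimens for alcohol biomarker testing will be collected at follow up visits". Treatment has begun by then. Under Enrollment, patients who meet all criteria receive "extended-release naltrexone as an intramuscular injection in the ED", and Medication storage and distribution confirms: "The initial dose will be given in UCSF ED".

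Index-visit sampling is described under Enrollment: "Enrollees will have blood and urine samples collected to screen for active opiate use including fentanyl, platelet counts, pregnancy, or significant liver disease". It is done "if no results are available in EHR", and its stated use is: "The results will be used to confirm inclusion/exclusion criteria are met". The Index ED visit section sets out the baseline data: contact and housing details, the ASI, the SIP-2R and timeline follow back. It mentions no specimen.

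**The concern.** A change outcome needs two measurements at defined times. For these two markers the protocol writes down only the later one. Staff who follow the written procedures would give the first injection without taking a biomarker specimen, and the loss would be permanent.

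The design makes this matter more. Everyone is treated and there is no randomization or blinding, and section IV relies on each patient being their own control. Without a pre-treatment value, a patient cannot play that role for these outcomes, and no concurrent group can stand in. The other four secondary outcomes rest on self-report in an open-label study whose authors already call the risk of bias substantial. PEth and urine ethyl glucuronide are the only laboratory measures of drinking among the secondary outcomes.

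**Working it through.** The plan gives no figure to reproduce here, and no sample-size formula applies. The check sets the outcome list against the procedures.

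| Secondary outcome (section IV) | Worded as change | Index measure written | Follow-up measure written |
|---|---|---|---|
| Drinks per week | no | yes, timeline follow back (Index ED visit) | substance use in general terms (Visit 2-3) |
| Heavy drinking days | no | yes, as above | as above |
| AUDIT | yes | yes (Enrollment) | yes (Visit 2-3) |
| SIP-2R | yes | yes (Index ED visit) | yes (Visit 2-3) |
| PEth | yes | **no** | yes, as a biomarker specimen (Visit 2-3) |
| Urine ethyl glucuronide | yes | **no** | yes, as above |

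**Counts.** Four of the six outcomes are worded as change. Of those four, two (AUDIT and SIP-2R) have both halves written, and the follow-up text says that the index questionnaires are repeated. The other two have only the later half: 2/4 = 50% of the change outcomes and 2/6 = 33% of all secondary outcomes.

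**Could the eligibility samples serve as the baseline?** Not as written, for three reasons:

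1. The tests listed are for opioids, platelets, pregnancy and liver disease; neither marker is among them.
2. Sampling is conditional, so an enrollee whose results are already in the record may give no specimen at all.
3. The only stated use of the results is to confirm eligibility.

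**What could be computed from the written schedule?**

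- Specimens before the first injection: 0.
- In-person follow-up visits on the three-injection schedule: at most 2 (visits 2 and 3). After visit 3, contact is by phone and no specimen is described.
- The only available difference is therefore visit 3 minus visit 2, about one month apart and both after treatment began. It exists only for patients who attend both visits.
- Participants with a change from a pre-treatment value: 0 of 25, and 0 of any replacements, whatever the attendance.

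The Participant Payment section refers to six monthly injection visits, while other sections give up to three doses. Those passages must be reconciled, but neither version places a biomarker specimen before the first injection.

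**The case against.** The strongest reply is that silence is not a decision to omit. The word change implies a starting value, and the protocol is loosely written elsewhere. For example, timeline follow back is named at the index visit but is missing from the list of repeated instruments, although two secondary outcomes depend on drinking quantity. The description of baseline data does not read as a closed list. The consent form, a natural place to list specimens, was not available for this check.

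Much of this stands. Nothing shows that the sponsor chose to do without a baseline, and the zero out of 25 is a statement about the written schedule, not a prediction. It does not remove the problem, however. The protocol does give a collection time for biomarkers, and that time is follow-up. Enrollment is planned around the clock, and the staff carrying it out need a written instruction.

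A second reply is that this is a small feasibility study and the biomarkers are secondary pilot data. That limits the consequence, and the point is rated accordingly. But section IV says the pilot data are for statistical analysis, and the timeline foresees a randomized follow-up trial. Whether paired biomarker specimens can be obtained is something a pilot should show.

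A third reply is that a baseline would not make the outcome sound: people enrolled during an ED visit may improve through regression to the mean alone. That is true. The repair makes change computable; it does not make it a controlled comparison.

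**Conclusion.** The concern holds. As the protocol is written, two of the six secondary outcomes, and two of the four worded as change, have no pre-treatment measurement. A change from a pre-treatment value would exist for 0 of the 25 planned participants on either marker.

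This rests on two assumptions: that staff follow the procedures as written, and that no document outside the protocol text schedules an index specimen. The change in ED visits, the feasibility outcomes and the sample size are unaffected. It should be corrected because the loss cannot be repaired at analysis, but it does not threaten the study's main purpose.

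**What to change.** In section II, under Enrollment and Index ED visit, schedule a blood sample for PEth and a urine sample for ethyl glucuronide from every enrollee before the first injection. State that this includes patients whose eligibility results come from the record. In section IV, define each change as the value at one named follow-up visit minus that baseline. If a baseline was always intended, the edit simply records it.

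**Cost.** Two assays per enrollee: 25 × 2 = 50, plus 2 for each replacement. That total assumes assays are run only once eligibility is confirmed. If they are run on everyone sampled during screening, people later found ineligible add to it, and 50 is a minimum. Enrollees who would otherwise give no index specimen need an added blood and urine sample; the protocol does not say how many that is. Index-visit sampling is already part of the procedures, so no new type of visit is needed. Section V names neither marker among its examples of tests paid for by the study, so the payer should be stated. Anyone enrolled before the change without these specimens will stay without a baseline and should be reported as such.

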Patients who miss scheduled follow up injection visits will be contacted and asked to reschedule their injection visit as soon as possible. If they are able to reschedule within 2 weeks then no changes to study procedure are necessary. If they are able to reschedule within 2-4 weeks then they will be asked if they have used any opiates (including fentanyl) in the past 7 days. If they have not used opiates in the past 7 days then they will resume treatment, provided they are not endorsing any signs or symptoms of liver injury. If they endorse signs or symptoms of liver injury they will undergo screening as outlined above. If they endorse using opiates then they will not be allowed to resume treatment through the study. If a patient is unable to reschedule a missed injection appointment within one month they will not be allowed to continue in the study. If a patient is unable to resume treatment through the study then they will be provided with alternative follow up options (see transition to ongoing care).

Participant Payment:

A 20-dollar gift card incentive will be used to encourage attendance at the 6 monthly follow up visits required for XR-Naltrexone injections. Gift cards will be given at each of the six visits. The total value of gift cards available to each participant during the study period is \$120.00. Gift cards will be issued for locations that do not sell alcohol (e.g. Starbucks coffee).

Study Subjects:

The target population is patients with frequent ED visits for alcohol related complaints who may benefit from ED-initiated XR-NTX. The accessible population is all people in the San Francisco Bay Area presenting to the ED with an alcohol related complaint. The study sample will be adult

patients presenting to the UCSF ED with active hazardous or high risk alcohol use and ≥ 4 ED visits in the past 12 months for alcohol related complaints.

Inclusion Criteria:

- Age ≥ 21
- AUDIT score ≥ 8
- Frequent emergency department visits, defined as: At least 3 emergency department visits for in the past 12 months, including the index visit.

Exclusion Criteria:

- Opioid use: currently receiving opioid analgesics, self-report of opioid use in past 7 days, current physiologic opioid dependence, patients in acute opioid withdrawal, urine toxicology screen positive for opiates including fentanyl
- History of hypersensitivity to naltrexone, polylactide-co-glycolide (PLG), carboxymethylcellulose, or any other components of the diluent

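### For injections 2 and 3, no stated opioid check can withhold the dose unless the visit is 2 to 4 weeks late

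*Combined protocol and SAP*

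**What the plan says.** The rules for late repeat injections are in Section II, Handling of missed injection visits. There are three steps.

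- Up to 2 weeks late: "If they are able to reschedule within 2 weeks then no changes to study procedure are necessary".
- 2 to 4 weeks late: if the visit can be rescheduled in this window, "then they will be asked if they have used any opiates (including fentanyl) in the past 7 days". The consequence is explicit: "If they endorse using opiates then they will not be allowed to resume treatment through the study".
- Later still: "If a patient is unable to reschedule a missed injection appointment within one month they will not be allowed to continue in the study".

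On-time visits, and by the first step visits up to 2 weeks late, follow Section II, Visit 2-3 study procedures. That text has questionnaires repeated at follow-up, including the Addiction Severity Index (ASI), to collect outcome data. On who gives the dose it says "Injections will be administered in an outpatient setting by an addiction community provider familiar with XR-Naltrexone", with the study emergency department (ED) as the alternative. It attaches no dosing decision to any opioid answer.

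At entry the position is strict. The Exclusion Criteria rule out anyone "currently receiving opioid analgesics, self-report of opioid use in past 7 days, current physiologic opioid dependence", as well as anyone in acute opioid withdrawal or with a positive urine screen. Section III, Risks and risk minimization strategy, names induced withdrawal in opiate-dependent patients as a risk of the drug. It says that urine screening and questioning will be used to exclude such patients.

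**The concern.** The entry screen shows that a participant was free of recent opioid use at the first dose. It says nothing about a month or more later. Someone may by then have resumed use, become dependent, or been prescribed opioids for pain. The last is not far-fetched: Section II, Index visit follow up, plans for opioid pain treatment during the study by giving participants a bracelet or card for other clinicians. Yet the entry exclusion for current opioid analgesics has no stated counterpart when injection 2 or 3 falls due.

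The 2-to-4-week rule shows that the sponsor already regards recent opioid use as relevant to a repeat dose. Under the plan as written, a participant 13 days late need not be asked, while one 15 days late who reports use is stopped. At stake is withdrawal induced by a study injection in a participant whose opioid use was not asked about before dosing.

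**Working it through.** This is a check of text, with simple arithmetic on timing. The plan gives no figure to reproduce.

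**Inputs.** Monthly dosing, up to three doses (Section II, Visit 2-3 study procedures). Lateness limits of 2 weeks, 4 weeks and one month (Section II, Handling of missed injection visits). Assumption: a month is 28 to 31 days, and lateness is counted from the scheduled date.

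**Formula.** Days since previous dose = month length + days late.

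| Timing of injection 2 or 3 | Days since previous dose | Stated opioid rule that controls the dose |
|---|---|---|
| On time | 28 to 31 | None |
| Up to 2 weeks late | up to 28 + 14 = 42, or 31 + 14 = 45 | None |
| 2 to 4 weeks late | up to 28 + 28 = 56, or 31 + 28 = 59 | 7-day question; stop if endorsed |
| More than one month late | beyond 28 + 28 = 56, or 31 + 31 = 62 | Not continued, whatever the answer |

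**Could another section supply the missing rule?**

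- *Visit 2-3 study procedures.* Substance use is recorded, so opioid use may well come up at an on-time visit. Nothing requires the answer to be looked at before the injection or says what a positive answer does to the dose.
- *Risks and risk minimization strategy, opioid paragraph.* It promises screening and questioning to exclude patients, but gives no visit, look-back period or hold action. It matches the entry criteria. If it governed every dose, the separate question at 2 to 4 weeks would be largely redundant.
- *Risks and risk minimization strategy, liver paragraph.* Symptoms are asked about at later injection visits, answers are reviewed weekly, and where tests are done further injections wait for the results. This is not a same-day check either, but it is a stated hold. Opioids have none outside the 2-to-4-week window.
- *Section V.* Urine drug and fentanyl screening appear as study-paid costs, with no schedule.

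None of these sets an opioid hold for an injection that is on time or up to 2 weeks late.

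**The case against.** The best counter-argument is that the grading looks deliberate. Checks tighten as time since the last antagonist dose grows, which is sensible if a recent dose still protects. That weakens the case for on-time doses. It does not settle the matter, because the protocol neither gives this reason nor states how long the blockade lasts, and the unchecked stretch runs on to 42 to 45 days.

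The general sentence on urine screening and questioning is not expressly limited to entry. Section V also calls urine drug screening research-only, whereas Section II, Enrollment, treats the entry tests other than pregnancy testing as routine care. One could infer some screening beyond entry. The two sections may simply disagree, however, and neither supplies a visit or an action.

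There are also real safeguards: injectors who know the drug, trained pharmacists available to ED nurses, the bracelet or card, an investigator reachable at any time, and monthly adverse-event collection. These make an unrecognised exposure less likely. None is a rule to withhold.

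Three stronger readings are tempting and should not be made.

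- A reader might infer that opioid use is never asked about at on-time visits. The repeated ASI contradicts this; what is missing is the link to dosing.
- A reader might infer from the restriction of REDCap to the study team that answers cannot reach a community injector. A database access rule does not limit clinical communication. Study staff carry each labelled community dose to the site (Section II, Medication storage and distribution), and the case manager coordinates the injections.
- A reader might count every repeat dose, 25 × 2 = 50, as exposed. That total includes doses given 2 to 4 weeks late, which already have a rule.

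**Conclusion.** The gap is real and limited. For injections 2 and 3, the only stated opioid rule that controls dosing applies at 2 to 4 weeks late. Visits on time or up to 2 weeks late, reaching 42 to 45 days since the last dose if a month is 28 to 31 days, have no opioid check tied to withholding. The concern is strongest at the late end of that stretch and for participants started on opioid analgesics between doses. It is weaker for on-time doses.

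The documents give no rate of opioid use, no expected share of late visits and no length of blockade, so no event rate can be stated and the size of the risk cannot be judged. The case for change rests on a risk that the protocol itself names, a question that it already uses, and a low cost. It should be fixed as a patient-safety improvement; confidence is medium.

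**What to change.** Add one step to Visit 2-3 study procedures, applying to every repeat injection whatever its timing. Before the dose, alongside the liver questions, ask the existing 7-day opioid question (fentanyl included) and whether the participant is currently taking opioid analgesics. On a yes to either, withhold that dose until the principal investigator or research fellow decides. Keep the present stop rule at 2 to 4 weeks and the one-month limit unchanged. Repeat urine screening is not needed for this fix.

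For visits on time or up to 2 weeks late, a hold pending a decision is preferable to automatic stopping, because a person who used opioids once is not necessarily dependent and should not lose alcohol treatment by default.

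The cost is a short form addition and a brief amendment. The downside is that some doses will be deferred or withheld, including for non-dependent users. This slightly affects two of the feasibility outcomes in Section IV, doses received and intervals between doses, so deferrals for this reason should be recorded and reported with them.
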